Investigators should be aware that special considerations are required for volume increases in patients with 2 infusion sites receiving a total dose (volume) of more than 50 mL. To ensure that volume increases do not exceed 25 mL/site, the infusions must be split between the 2 syringes, such that each infusion site will receive a different total volume. For example, if a patient is receiving a total dose of 60 mL divided equally between 2 infusion sites (eg, 30 mL/site), the first syringe could be increased to an infusion volume of 50 mL (an increase of 20 mL) and the

Name of Sponsor/Company: Octapharma USA, [name]	
Name of Investigational Product: CUTAQUIG	Protocol Identification Code: SCGAM-06
Name of Active Ingredient: Human Normal Immunoglobulin	Date of Final Protocol: 28-Aug-2019

second syringe would have an infusion volume of 10 mL. If this is tolerated, the next infusion volume increase could be 60 mL at 1 infusion site (an increase of 10 mL) and remain below the maximum allowed volume increase of 25 mL/site.

Cohort 2 (increased infusion rate - patients will receive CUTAQUIG weekly and increase infusion rates every 4 weeks): Patients will return to the clinic for the Treatment Period Baseline Visit, at which they will receive the same body-weight dependent (mg/kg) dose of CUTAQUIG but the infusion rate per site will be increased up to a maximum allowed flow rate increase per infusion site of 25 mL/hr/site for patients ≥ 40 kg or 10 mL/hr/site for patients < 40 kg. Patients will receive this new flow rate for 4 weekly infusions (Treatment Period Baseline and Weeks 1, 2, and 3), and return to the clinic at Week 4 for their next infusion at an increased infusion rate. This cycle will continue, with maximum allowed flow rate increases per infusion site of up to 25 mL/hr/site for patients ≥ 40 kg or up 10 mL/hr/site for patients < 40 kg every 4th infusion until reaching either: 1) a maximum flow rate (100 mL/hr/site) or the maximum flow rate achievable by the pump, or 2) the maximum tolerated flow rate (maximum flow rate based on Investigator's decision of patient's tolerance) – whichever is reached first.

Note: Clinical sites are encouraged to enroll patients that are either currently infusing with 24-gauge needle sets or willing to switch to 24-gauge needle sets. Patients using 27-gauge needles will not be able to achieve adequate infusion rates for this cohort as the needle gauge will not allow for this.

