- Baseline: Increase infusion rates up to 25 mL/hr/site. This can be accomplished by increasing the tubing set, needle gauge, and adjusting pump rates (if applicable). Continue with the same infusion parameters at Weeks 1, 2, and 3.
- Week 4: If the infusion rate increase administered at Baseline through Week 3 is tolerated, increase infusion rates again by up to 25 mL/hr/site for patients ≥ 40 kg or 10 mL/hr/site for patients < 40 kg. This can be accomplished by increasing the tubing set, increasing needle gauge, or adjusting pump rates (if applicable). Continue with the same infusion parameters at Weeks 5, 6, and 7.
- Week 8: If the infusion rate increase administered at Week 4 through Week 7 was tolerated, increase infusion rates again by up to 25 mL/hr/site for patients ≥ 40 kg or 10 mL/hr/site for patients < 40 kg. This can be accomplished by revising the tubing, increasing needle gauge, or adjusting pump rates (where applicable). Continue with the same infusion parameters at Weeks 9, 10, and 11.
- Weeks 12, 16 and 20: If necessary and if the infusion rate increase administered at Week 8 through Week 11 was tolerated, the patient should continue the rate increase process as described above.

Note: Clinical sites are encouraged to enroll patients that are either currently infusing with 24-gauge needle sets or willing to switch to 24-gauge needle sets. Patients using 27-gauge needles will not be able to achieve adequate infusion rates for this cohort as the needle gauge will not allow for this.

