If ADRs occur during an infusion, the patient may go back to the previous regimen that was tolerated if deemed necessary by the Investigator and/or patient; this would include decreasing the infusion flow by decrease tubing size, increasing needle gauge, or adjusting pump rates. This tolerated infusion regimen will continue until the next study visit, at which the patient would attempt to again increase the infusion rate. If ADRs occur again, the patient may again go back to the previous stable regimen if deemed necessary until the next study visit. If multiple attempts to increase rate are unsuccessful, Investigators should continue attempting to increase rates, but by lower amounts than those previously attempted. Investigators should refer to the provided flow rate tubing calculators to identify optimal rate parameters. Following unsuccessful attempts to increase infusion rate, the Investigator and patient can cease or hold additional attempts and the patient may remain in the study; however, every effort to increase infusion rates should be attempted.

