5.5.3 Infusion Flow Rates

- The maximum recommended flow rate is 100 mL/hr/infusion site.
- The maximum infusion rate for all sites combined is 240 mL/hr.
- Infusion volumes and flow rates may only be increased if the previous 2 administrations were tolerated by the patient, and deemed appropriate by the Investigator.
- Infusion volume and flow rate should be increased gradually as tolerated to prevent infusion site reactions. See the parameters listed in Table 6.

Table 6: Infusion Volume and Flow Rate by Patient Weight

	Recommended Increase for Patients <40 kg	Recommended Increase for Patients ≥ 40 kg
Infusion Volume mL/site per infusion cycle	Approximately ≤ 10 mL/site	Approximately ≤ 25 mL/site
Infusion Flow Rate mL/hour/site per infusion cycle	≤ 10 mL/hour/site	≤ 25 mL/hour/site

Note: To account for non-precision flow rates of pumps, actual flow rate increases will be dependent on tubing size, number of infusion sites, and needle gauge. Minor deviations in flow rates (<2 mL/site) would not be considered protocol deviations.

Instructions for performing volume increases in Cohort 1 patients who are using 2 infusions sites with a total volume of ≥ 50 mL are provided in Section 3.3.2.

If AEs occur during an infusion, the flow rate and volume may be reduced if deemed necessary by the Investigator and/or patient to the previous flow rate and volume at which no AE occurred. If appropriate, the infusion may be interrupted until symptoms subside. The infusion may then be resumed at a flow rate or volume tolerated by the patient.

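### Cohort 2 rate-increase steps in Protocol Section 3.3.2 give the needle-gauge direction the wrong way round: the same action is listed both to raise and to lower flow

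*Protocol*

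**What the plan says.** The Cohort 2 part of Protocol Section 3.3.2 sets out stepwise rate increases and, for each step, the means of achieving them.

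- **Baseline:** "This can be accomplished by increasing the tubing set, needle gauge, and adjusting pump rates (if applicable").
- **Week 4:** "This can be accomplished by increasing the tubing set, increasing needle gauge, or adjusting pump rates (if applicable").
- **Week 8:** "This can be accomplished by revising the tubing, increasing needle gauge, or adjusting pump rates (where applicable").
- **Weeks 12, 16 and 20:** no means are listed. The patient continues the process set out in the preceding bullets.

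A note directly below the bullets, also given in the Study Outline, says: "Clinical sites are encouraged to enroll patients that are either currently infusing with 24-gauge needle sets or willing to switch to 24-gauge needle sets". It continues: "Patients using 27-gauge needles will not be able to achieve adequate infusion rates for this cohort".

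The next paragraph covers adverse drug reactions during an infusion. The patient may return to the last tolerated regimen, which includes "decreasing the infusion flow by decrease tubing size, increasing needle gauge, or adjusting pump rates". The same paragraph adds: "Investigators should refer to the provided flow rate tubing calculators to identify optimal rate parameters".

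The note to Table 6 in Section 5.5.3 says that "actual flow rate increases will be dependent on tubing size, number of infusion sites, and needle gauge".

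**The concern.** An increase in needle gauge is offered as a way to speed the infusion at Weeks 4 and 8, and as a way to slow it after a reaction. One action cannot do both.

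This is a current dosing instruction, not background text. Flow rate is the Cohort 2 intervention, and safety and tolerability at increased flow rates is a co-primary objective (Protocol Section 2.1). A site that followed the escalation bullets literally, in gauge numbers, would fit a narrower needle at a step meant to raise the rate. A site that took from the bullets that a higher gauge means a wider bore, and carried that meaning into the next paragraph, would widen the needle when it meant to slow the infusion.

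**Working it through.** No arithmetic applies and the plan gives no figure to reproduce. The check is whether any single meaning of the phrase makes all the sentences true together.

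**Step 1. Fix the direction from the protocol itself.** The gauge note encourages 24-gauge sets for the cohort that needs high flow and rules 27-gauge out as too restrictive. So going from 27 to 24 (number down) raises achievable flow, and going from 24 to 27 (number up) lowers it. No outside source is needed.

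**Step 2. Test each sentence under both meanings.**

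| Place in Section 3.3.2, Cohort 2 | Purpose | Increase = higher gauge number | Increase = wider bore |
|---|---|---|---|
| Baseline bullet (elliptical) | raise flow | wrong direction, by implication | right |
| Week 4 bullet | raise flow | wrong direction | right |
| Week 8 bullet | raise flow | wrong direction | right |
| Step-back after reactions | lower flow | right | wrong direction |

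Neither column is right throughout, so at least one sentence is wrong under any consistent reading.

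**Step 3. Decide which side to correct.** The gauge note speaks in gauge numbers (24 and 27). In those terms the step-back sentence agrees with the note, and the Week 4 and Week 8 bullets do not.

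**Step 4. Count the places.** The explicit phrase occurs three times in the protocol: twice to raise flow (Weeks 4 and 8) and once to lower it (step-back). At Baseline the verb governing the tubing set appears to govern needle gauge too, so that bullet points the same way in looser wording. Weeks 12, 16 and 20 carry no needle wording of their own but inherit it by reference. Cohorts 1 and 3 mention adjusting or changing the needle gauge without giving a direction, so they are unaffected.

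**Step 5. Trace the consequence.** Section 5.5.3 confirms that needle gauge affects the rate actually delivered, so the direction matters where the lever is used. On the analysis side, Protocol Section 9.1 states that the co-primary endpoints are analysed descriptively, with a confirmatory test in Cohort 3 only. The needle wording enters no estimate, margin, sample size or test.

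**The case against.** The strongest counter-argument is that the escalation bullets use a size sense. They pair needle gauge with increasing the tubing set, and Baseline uses one verb for both. Read that way, all three bullets agree with each other and with the gauge note, and the only slip is in the step-back sentence, which is already ungrammatical. The secure statement would then be that one term is used in two opposite senses. Part of this stands: the conflict is in terminology, and the wider-bore reading is a fair guess at what the authors meant by the bullets. But it moves the error to the post-reaction instruction rather than removing it, and the protocol elsewhere gives needles by gauge number. Both places should therefore state the direction.

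The second argument is that the documents already contain the practical risk, and this largely stands.

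- At Weeks 4 and 8 the needle is one of three alternatives.
- The gauge note, with its named gauges, sits immediately below the bullets.
- Flow-rate tubing calculators are provided.
- At the required visits the infusion is given on site and technique is assessed (Section 6.1.3).
- Each step has a limit in mL/hr/site, 25 or 10 by body weight (Table 6). These limits are ceilings, so they would not by themselves flag too small an increase. A rate that fell would still contradict the purpose of the step.
- The SAP summarises flow rates (Section 8.4) and tabulates temporally associated events against infusion flow rate (Section 10.1), so an escalation that failed could be seen in the data.

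A reader might go further and infer that Cohort 2 escalation, or the safety data at high rates, is compromised, or try to count affected patient-steps from the planned 15 patients. The documents do not support either. Use of the needle lever is not recorded anywhere in the plan. Fifteen is only a minimum. The later steps inherit the wording, so counting Weeks 4 and 8 alone would not give an upper bound. Patients who follow the encouragement to use 24-gauge sets may have their needle settled at the start, leaving tubing and pump as the levers.

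**Conclusion.** The point holds as a wording error in a current dosing instruction. In gauge numbers, the Week 4 and Week 8 bullets are reversed, Baseline points the same way by implication, and Weeks 12, 16 and 20 inherit the wording. The step-back sentence has the right direction.

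The conclusion rests on one assumption, which the protocol's own note supports: gauge means gauge number. Without it, the conflict remains and only its location changes.

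The effect is operational and small, and cannot be expressed as a number of patients or infusions. If the bullets were followed literally, the likely result would be slower escalation and less exposure at the higher rates, not a rate above a limit. The opposite outcome, faster flow after a reaction, would require a site to apply the wider-bore meaning to a sentence whose stated purpose is to decrease flow. No analysis, sample size or confirmatory test is affected. This is an optional correction that is worth making because it costs almost nothing.

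**What to change.** In the Baseline, Week 4 and Week 8 bullets of Cohort 2 in Protocol Section 3.3.2, replace the needle wording with *using a larger-bore needle (lower gauge number, e.g. 24-gauge)*. Weeks 12, 16 and 20 then inherit the corrected text. In the step-back sentence, keep the direction and add *(higher gauge number, smaller bore)* after the needle wording. Send sites a one-line clarification to the same effect.

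The cost is three short replacements, one parenthesis and one site message. No visit, data item, sample size or analysis changes, and the SAP needs no edit.

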3.3.3 Control Group(s)

Not applicable: all patients will receive active treatment with CUTAQUIG.

3.3.4 Study Parameters

The outcome measures in this study are consistent with previous studies of other IVIG or SCIG products and are also in compliance with the US FDA Guidance for Industry on Safety, Efficacy, and Pharmacokinetic Studies to Support Marketing of Immune Globulin Intravenous (Human) as Replacement Therapy for Primary Humoral Immunodeficiency.[25]

QoL questionnaires (SF-10 Health Survey from parent or guardian of patients <14 years of age and SF-36 Health Survey in patients ≥14 years of age) used in this study are standardized, validated instruments that have been widely used in clinical studies, including studies in the PI disease population.

Property of Octapharma. Do not copy or distribute without written permission.

4 STUDY POPULATION

4.1 Population Base

Approximately 65 male or female patients, between 2 years and 75 years of age, suffering from PI will be eligible for inclusion.

4.1.1 Inclusion Criteria

Patients who meet all of the following criteria are eligible for the study:

1. Age \geq 2 years and \leq 75 years.
2. Confirmed diagnosis of primary immunodeficiency (PI) disease as defined by ESID and PAGID and requiring immunoglobulin replacement therapy due to hypogammaglobulinaemia or agammaglobulinaemia. **Note:** The exact type of PI disease will be recorded.
3. Established on a consistent or stable mg/kg dose of any SCIG treatment for a minimum of 3 months prior to Screening. **Note:** patients entering Cohort 3 must be on weekly SCIG infusions for a minimum of 12 weeks.
4. Availability of the Immunoglobulin G (IgG) trough levels of 2 previous SCIG infusions within 1 year of Screening, with 1 trough level obtained within 3 months prior to enrollment, and maintenance of trough serum IgG levels \geq 5.0 g/L in 2 previous infusions. Patients with no prior IgG trough level within 3 months prior to enrollment may use the Screening IgG trough level as their 2nd reading.
5. Voluntarily given, fully informed, signed informed consent. For patients under the legal age of consent, voluntarily given, fully-informed, signed informed consent will be provided by patient's parent or legal guardian, and assent will be provided by patient (per age-appropriate Institutional Review Board [IRB] requirements)
6. Females of childbearing potential, who are not nursing and have no plans for pregnancy during the course of the study, must have been using at least 1 acceptable form of birth control for a minimum of 30 days prior to the Screening visit and must agree to use at least 1 acceptable method of contraception for 30 days after the last dose of CUTAQUIG. Acceptable methods include: intrauterine device (IUD), hormonal contraception, male or female condom, spermicide gel, diaphragm, sponge, or cervical cap, or abstinence.
7. For female patients of child-bearing potential, a negative result in a urine pregnancy test conducted at the Screening visit.
8. Willingness to comply with all aspects of the protocol, including blood sampling, for the duration of the study.

4.1.2 Exclusion Criteria

Patients who meet any of the following criteria are *not* eligible for the study:

1. Evidence of an active infection within 4 weeks of Screening or during the Screening Period.

2. Current or clinically-significant history of any cardiovascular, respiratory, hepatic, renal, gastrointestinal, endocrine, neurological, immunological (excluding PI), hematologic, and/or psychiatric disorder(s), or a history of any other illness that, in the opinion of the Investigator, might confound the results of the study, or pose additional risk to the patient by participation in the study.
3. Known history of adverse reactions to immunoglobulin A (IgA) in other products.
4. Body mass index (BMI) $>40 \text{ kg/m}^2$ for patients entering Cohort 2 or Cohort 3. There are no BMI restrictions for Cohort 1.
5. Ongoing history of hypersensitivity or persistent reactions to blood or plasma derived products, or any component of the investigational product (such as Polysorbate 80).
6. Requirement of any routine premedication for IgG administration.
7. History of malignancies of lymphoid cells and immunodeficiency with lymphoma.
8. Severe liver function impairment (aspartate aminotransferase [AST] or alanine aminotransferase [ALT] >3 times above upper limit of normal).
9. Known protein-losing enteropathies or clinically significant proteinuria.
10. Presence of renal function impairment or predisposition for acute renal failure (eg, any degree of pre-existing renal insufficiency or routine treatment with known nephritic drugs).
11. Treatment with oral or parenteral steroids for ≥ 30 days, or when given intermittently or as bolus at daily doses $\geq 0.15 \text{ mg/kg}$ when taken within 30 days of Screening. **Note:** Short or intermittent courses of steroids (ie, a steroid burst) of $>0.15 \text{ mg/kg/day}$ is allowed for treatment of a short-term condition such as an asthma exacerbation.
12. Treatment with immunosuppressive or immunomodulatory drugs (except Omalizumab).
13. Use of HYQVIA (Immune Globulin Infusion 10% [Human] with Recombinant Human Hyaluronidase) within 3 months prior to first CUTAQUIG infusion.
14. Live viral vaccination (such as measles, rubella, mumps, and varicella) within 2 months prior to first CUTAQUIG infusion.
15. Exposure to blood or any blood product or derivative, other than sub-cutaneous IgG used for regular PI disease treatment, within 3 months before the first CUTAQUIG infusion.
16. Treatment with any investigational medicinal product within 3 months prior to first CUTAQUIG infusion. **Note:** Patients participating in Study SCGAM-03 will be allowed to enter this study without the 3-month waiting period for an Investigational Product. Patients receiving another investigational SCIG product within 3 months prior to the first CUTAQUIG infusion may be considered for enrollment after Sponsor approval.
17. Presence of any condition that is likely to interfere with the evaluation of CUTAQUIG or satisfactory conduct of the trial.
18. Known or suspected to abuse alcohol, drugs, psychotropic agents, or other chemicals within the past 12 months prior to first CUTAQUIG infusion.

19. Known active or chronic hepatitis B, hepatitis C or HIV infection. Past hepatitis B or hepatitis C infection that has been cured is allowed.

4.2 Prior and Concomitant Therapy

Details on any relevant medications taken within 8 weeks prior to enrollment must be recorded in the electronic Case Report Form (eCRF). The following medications that are considered relevant for the previous 8 weeks include:

- Antibiotics
- Corticosteroids,
- Premedication (if used)
- Immunosuppressive or immunomodulatory drugs
- blood or any blood product or derivative
- IVIG, SCIG, or other IgG preparations

All new and ongoing concomitant medications taken during the Screening Period and throughout the study will be captured in the eCRF.

4.2.1 Permitted Concomitant Therapy

Local anesthetics (EMLA® or lidocaine cream, plaster, or other similar products) to reduce pain associated with needle insertion are allowed. The use of such medication(s) must be recorded.

Routine premedication to alleviate potential tolerability problems is not allowed during the study. However, patients who experience 2 consecutive TEAEs during the study (that are likely to be prevented by premedication) are permitted to receive antipyretics, antihistamines, or antiemetic drugs. Non-steroidal anti-inflammatory drugs should be avoided.

4.2.2 Forbidden Concomitant Therapy

Treatment with any IMP (other than IgG products [including CUTAQUIG] administered during Study SCGAM-03) within 3 months before first infusion of CUTAQUIG, or during the study, is forbidden. Patients receiving another investigational SCIG product within 3 months prior to the first CUTAQUIG infusion may be considered for enrollment after Sponsor approval.

Administration of any blood- or plasma-derived product is forbidden during the study and should only be given for emergency reasons. Patients will be withdrawn from the study if IgG preparations other than CUTAQUIG are administered during the study.

Premedication for study CUTAQUIG infusions shall not be given, with the exception of permitted therapy as stated above (for patients with 2 consecutive TEAEs). Corticosteroids shall not be given as a premedication to alleviate potential tolerability problems.

Treatment with oral or parenteral steroids for ≥ 30 days (long term daily > 0.15 mg of prednisone equivalent/kg/day). Exception: Requirement for short or intermittent courses (ie, a steroid burst) of > 0.15 mg/kg/day is allowed for treatment of a short-term condition such as an asthma exacerbation.

Immunosuppressive and immunomodulatory drugs are forbidden, with the exception of Omalizumab.

CUTAQUIG must not be mixed with other medicinal products.

